2.5.3 Handling of remaining intercurrent events of primary estimand

No remaining intercurrent events.

2.5.4 Handling of missing values not related to intercurrent event

Patients with missing PCR evaluations at 24 weeks will be considered as non-responders. However, if the 24-week PCR evaluation is missing, but both a PCR evaluation at 16 weeks and a PCR evaluation at 36 weeks indicate MMR, the 24-week assessment is imputed as a 'Response', assuming that MMR is maintained between 16 and 36 weeks.

2.5.5 Sensitivity analyses

The following sensitivity analyses will be performed:

- The CMH chi-square test of MMR rate at 24 weeks will be repeated stratifying by the stratum recorded in the CRF (MCyR vs no MCyR at baseline).
- Due to the COVID-19 (Coronavirus) pandemic, there is a risk that planned hospital visits are cancelled, potentially resulting in missing PCR evaluations. In order to assess the impact of COVID-19 (including potential missing data) on the primary endpoint, the

CMH chi-square test of MMR rate at 24 weeks will be repeated on the FAS excluding the patients with planned 24-week visit (start of study treatment + 161 days) after the start date of COVID-19 epidemic. As per Novartis guidance, the start date, in a given country or region, is being defined as the approximate time point at which, according to the WHO situation reports and the Johns Hopkins database, the number of confirmed COVID-19 infections started to increase significantly (around 100 confirmed cases) and/or governments started to take measures (such as stay-at-home orders) to contain the epidemic, whichever occurred first (China: January 1, 2020; South Korea: February 20, 2020; Japan: February 21, 2020; Italy: February 23, 2020 and Rest of the World: March 1, 2020).

- The CMH chi-square test of MMR rate at 24 weeks will be repeated without the imputation rule used in the main analysis in case of missing PCR evaluations at 24 weeks.

2.5.6 Supplementary analyses

Additional supplemental logistic regression and subgroup analyses are described in [Section 2.14](#).

Assess whether the efficacy of asciminib (40 mg bid) is superior to bosutinib (500 mg qd) in CML patients in chronic phase, without T315I or V299L mutation detected at Week 1 Day 1 visit and previously treated with 2 or more tyrosine kinase inhibitors, with regards to achieving MMR at 24 weeks while on study treatment and without meeting any treatment failure criteria (defined in [section 5.4.4](#)) prior to 24 weeks, regardless of dose modification, dose interruption, or deviation in any intake of concomitant medications.

The corresponding estimand attributes are the same as the ones of the primary estimand except that the population excludes patients detected with T315I or V299L at Week 1 Day 1 visit (As per protocol, these patients were discontinued from study treatment when the mutation results became available).

The CMH chi-square test of MMR rate at 24 weeks will be repeated on the FAS excluding patients detected with T315I or V299L at Week 1 Day 1 visit.

2.6 Analysis of the key secondary objective/estimand

The key secondary clinical question of interest is: Is the efficacy of asciminib (40 mg bid) superior to bosutinib (500 mg qd) in CML patients in chronic phase, previously treated with 2 or more tyrosine kinase inhibitors, with regards to achieving MMR at 96 weeks while on study treatment and without meeting any treatment failure criteria (defined in [section 5.4.4](#)) prior to 96 weeks, regardless of dose modification, dose interruption, or deviation in any intake of concomitant medications.

The key secondary estimand is described by the following attributes:

Population: CML patients in chronic phase, previously treated with 2 or more tyrosine kinase inhibitors. Further details about the population are provided in Section 5 of the protocol.

Endpoint: Major Molecular Response (MMR) achieved at 96 weeks while being treated without meeting any treatment failure criteria (defined in [section 5.4.4](#)) prior to 96 weeks. A patient will be counted as having achieved MMR at 96 weeks if he/she meets the MMR criterion (BCR-

ABL ratio $\leq 0.1\%$) at 96 weeks while on study treatment unless the patient met any treatment failure criteria (defined in [section 5.4.4](#)) prior to 96 weeks.

Intercurrent events:

- Treatment discontinuation (i.e. having performed an EOT visit) prior to 96 weeks due to any reason (e.g. intolerance, treatment failure, death, etc.): non response
- Meeting any treatment failure criteria (defined in [section 5.4.4](#)) prior to 96 weeks: non response
- Dose modification, dose interruption, or deviation in any intake of concomitant medications: ignore (treatment policy strategy)

Treatment of interest: the randomized treatment (the investigational treatment asciminib or the control treatment bosutinib) received for at least 96 weeks with or without dose modification, dose interruption or deviation in any intake of concomitant medications. Further details about the investigational treatment and control treatment are provided in Section 6 of the protocol.

Handling of remaining intercurrent events : no other IE foreseen

The summary measure: difference in MMR rate and its 95% confidence interval at week 96 between the two treatment arms

The analysis of the key secondary objective will be performed at the time of the 96-week analysis.

2.6.1 Key secondary endpoint/estimand

The key secondary endpoint is MMR achieved at 96 weeks while on study treatment without meeting any treatment failure criteria (defined in [section 5.4.4](#)) prior to 96 weeks. A patient will be counted as having achieved MMR at 96 weeks if he/she meets the MMR criterion (BCR-ABL ratio $\leq 0.1\%$) at 96 weeks while on study treatment unless the patient met any treatment failure criteria (defined in [section 5.4.4](#)) prior to 96 weeks.

MMR will be considered as a binary variable with patients achieving MMR grouped as 'responders' and patients not achieving MMR grouped as 'non responders'. Only patients with MMR at 96 weeks are considered responders. In other words, any patient who achieves MMR before 96 weeks, but is no longer in MMR at 96 weeks, will be considered as a non-responder in this key secondary analysis.

Patients discontinuing treatment (i.e. having performed an EOT visit) prior to 96 weeks due to any reason (e.g. intolerance, treatment failure, death, etc.) and patients meeting any treatment failure criteria (defined in [section 5.4.4](#)) prior to 96 weeks will be considered as not having achieved MMR at 96 weeks.

2.6.2 Statistical hypothesis, model, and method of analysis

The null hypothesis is that there is no difference between the treatment groups with respect to MMR rate at 96 weeks. Following a gatekeeping procedure to control the overall alpha level, only if the primary endpoint is significant, formal statistical testing of the key secondary endpoint with two-sided 5% level of significance will be performed using the CMH chi-square

test, stratified by the randomization stratification factor, i.e. cytogenetic response status (MCyR vs no MCyR) at screening.

MMR rate and its 95% confidence interval based on the Pearson-Clopper method will be presented by treatment group. The 95% confidence interval for the difference in MMR rate between treatment groups will be provided using the Wald method. The Mantel-Haenszel estimate of the common risk difference and the corresponding 95% confidence interval will also be presented.

2.6.3 Handling of remaining intercurrent events of primary estimand

No remaining intercurrent events.

2.6.4 Handling of missing values not related to intercurrent event

Patients with missing PCR evaluations at 96 weeks will be considered as non-responders. However, if the 96-week PCR evaluation is missing, but both a PCR evaluation at 84 weeks and a PCR evaluation at 108 weeks indicate MMR, the 96-week assessment is imputed as a 'Response', assuming that MMR is maintained between 84 and 108 weeks.

2.6.5 Sensitivity analysis

- In order to assess the impact of COVID-19 (including potential missing data) on the key secondary endpoint, the CMH chi-square test of MMR rate at 96 weeks will be repeated on the FAS excluding the patients with planned 96-week visit (start of study treatment + 665 days) between the start date of the COVID-19 epidemic (China: January 1, 2020; South Korea: February 20, 2020; Japan: February 21, 2020; Italy: February 23, 2020 and Rest of the World: March 1, 2020) and its end date (to be defined in the future).
- The CMH chi-square test of MMR rate at 96 weeks will be repeated without the imputation rule used in the main analysis in case of missing PCR evaluations at 96 weeks.

2.7 Analysis of secondary efficacy objective(s)

The other secondary efficacy objective is to compare additional parameters (defined below) of the efficacy of asciminib versus bosutinib.

2.7.1 Secondary endpoints

2.7.1.1 Molecular response

MMR rates at all scheduled data collection time points, i.e., the protocol-planned visits except for 24 weeks and 96 weeks which are already covered by primary and key secondary endpoints. Such rates are defined as the proportion of patients with MMR at the respective time points.

MMR rates by all scheduled data collection time points, i.e., the protocol-planned visits. These are cumulative MMR rates by time points and are defined as the proportion of patients who achieve MMR at or before specified visits, i.e. if a patient achieves an MMR but then loses it before or at a specific visit, he/she will still be classed as achieving MMR by that specific time point.

Molecular response category at specific time points, i.e., the protocol-planned visits. Categories of molecular response are defined in Appendix.

Molecular response category by specific time points, i.e., the protocol-planned visits. This is defined as the best (lowest) molecular response category up to the specific time points.

Time to MMR (in weeks) is defined as: (date of first documented MMR - date of randomization + 1)/7.

Duration of MMR is defined for patients in the MMR Responder Set as the time between the date of the first documented MMR and the end date of MMR, i.e. the earliest date of confirmed loss of MMR, progression to accelerated phase (AP)/blast crisis (BC), or CML-related death.

Loss of MMR and progression to accelerated phase (AP)/blast crisis (BC) are defined in Appendix.

For patients for whom none of the events above is reported, the duration will be censored (see [Section 2.7.3](#)). The duration of MMR (in weeks) is calculated as: (end date or censoring date of MMR - date of first MMR + 1)/7.

2.7.1.2 Cytogenetic response

At each assessment time point the cytogenetic response status of each patient is classified as complete, partial, major, minor, minimal response and none (a review of a minimum of 20 metaphases is required):

- Complete response (CCyR): 0% Philadelphia chromosome positive (Ph+) metaphases
- Partial response (PCyR): >0 to 35% Ph+ metaphases
- Major response (MCyR = CCyR + PCyR): 0 to 35% Ph+ metaphases
- Minor response (mCyR): >35 to 65% Ph+ metaphases
- Minimal response: >65 to 95% Ph+ metaphases
- None: >95 to 100% Ph+ metaphases.

As per protocol, bone marrow aspirate for cytogenetic analyses will be performed as long as subjects have not achieved MMR. Therefore, in case no bone marrow aspirate was performed but the subject is in MMR at a specific time-point, the subject is considered to have achieved CCyR at that time-point. The date of CCyR is imputed by the date of MMR at the same scheduled time-point.

CCyR rates at all scheduled data collection time points, i.e., the protocol-planned visits. Such rates are defined as the proportion of patients in CCyR at the respective time points among patients in the CCyR Analysis Set, which excludes patients who are in CCyR at baseline.

CCyR rates by all scheduled data collection time points, i.e., the protocol-planned visits. Such rates are defined as the proportion of patients who achieve CCyR at or before the respective time points among patients in the CCyR Analysis Set.

Cytogenetic response category at specific time points, i.e., the protocol-planned visits. At each assessment time point the cytogenetic response status of each patient is classified as complete, partial, major, minor, minimal response and none (a review of a minimum of 20 metaphase is required) as defined in Appendix.

Cytogenetic response category by specific time points, i.e., the protocol-planned visits. This is defined as the best (lowest) cytogenetic response category up to the specific time points.

Time to CCyR (in weeks) is defined for patients as: (date of first documented CCyR - date of randomization + 1)/7.

Duration of CCyR is defined for patients in the CCyR Responder Set as the time between date of first documented CCyR and the end date of CCyR, i.e. the earliest date of loss of CCyR, progression to AP/BC, or CML-related death. Loss of CCyR and progression to AP/BC are defined in Appendix. For patients for whom none of the events above is reported, the duration will be censored (see [Section 2.7.3](#)). The duration of CCyR (in weeks) is calculated as: (end date or censoring date of CCyR - date of first CCyR + 1)/7.

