CCyR rates at specific time points: Patients discontinuing the randomized treatment prior to a specific time point due to any reason will be considered as non-responders for that time point.

CCyR rates by specific time points: This will be handled similarly as MMR, but with CCyR instead.

Cytogenetic response at specific time points: This will be handled similarly as molecular response category.

Cytogenetic response category by specific time points: This will be handled similarly as molecular response category.

Time to CCyR: For patients in the CCyR analysis set who have not experienced any CCyR, the time will be censored in the same manner as Time to MMR.

Duration of CCyR: For patients in the CCyR responder set who have not experienced any event (loss of CCyR, progression to AP/BC, or CML-related death) the duration will be censored at the last cytogenetic assessment date on treatment or the last PCR evaluation on treatment indicating MMR, whichever is the latest.

TTF: For patients in the FAS who have not reached treatment failure, their TTFs will be censored at the time of their last study assessment (PCR, cytogenetic, hematologic or extramedullary) before the cut-off date.

PFS: For patients who have not experienced an event (disease progression to AP/BC or death from any cause), their PFS times will be censored at the date of last study assessment (PCR, cytogenetic, hematologic or extramedullary) before the cut-off date, regardless of subsequent intake of treatment(s) after randomization.

OS: Patients who are alive at the time of the analysis data cutoff date will be censored at the date of last contact (see [Section 2.1.1](#)) before the cut-off date, regardless of subsequent intake of treatment(s) after randomization.

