5.1.2.1 Other imputations

Incomplete date of initial diagnosis of cancer

Missing day is defaulted to the 15th of the month and missing month and day is defaulted to 01-Jan.

Stratum reported in the CRF

This will be derived from the Bone Marrow Aspirate data recorded in the corresponding eCRF pages at baseline. In some case the baseline sample may be missing or not evaluable (i.e. <20 metaphases).

The following imputation rule will be applied to derive the missing or non evaluable values:

- Major cytogenetic response (MCyR) (0 to 35% Ph+ metaphases) will be assumed if BCR-ABL1 levels $\leq 10\%$ (IS).

Rationale:

ELN 2013 recommendations are providing treatment milestones with response categories for cytogenetic and molecular response, which we can refer to for the imputation:

6 mo	BCR-ABL1 <1% and/or Ph+ 0	BCR-ABL1 1-10% and/or Ph+ 1-35%	BCR-ABL1 >10% and/or Ph+ >35%
------	---------------------------------	---------------------------------------	-------------------------------------

MCyR is roughly corresponding to BCR-ABL1 levels $\leq 10\%$ (IS) (Ross et al 2009).

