5.4.2 Cytogenetic response

Cytogenetic response will be based on the percentage of Ph⁺ metaphases in the bone marrow. Cytogenetic evaluations will be considered for response assessment only if the number of metaphases examined is ≥ 20 in each bone marrow sample. As per protocol, fluorescent *in-situ* hybridization (FISH) assessments will not be considered for any evaluation of cytogenetic response during treatment.

Cytogenetic response is categorized as follows (a review of a minimum of 20 metaphases is required):

- Complete response (CCyR): 0% Philadelphia chromosome positive (Ph⁺) metaphases
- Partial response (PCyR): >0 to 35% Ph⁺ metaphases
- Major response (MCyR = CCyR + PCyR): 0 to 35% Ph⁺ metaphases
- Minor response (mCyR): >35 to 65% Ph⁺ metaphases
- Minimal response: >65 to 95% Ph⁺ metaphases
- None: >95 to 100% Ph⁺ metaphases.

If bone marrow aspirate blast percentage is provided as ‘ $<X$ ’ (i.e. below limit of detection), the numeric value is set to X for summary tables. In the listing ‘ $<X$ ’ will be presented.

Complete cytogenetic response (CCyR)

CCyR is defined as a value of 0% Ph⁺ metaphases in bone marrow.

CCyR will be considered as a binary variable with patients achieving CCyR grouped as ‘responders’ and patients not achieving CCyR, patients with missing cytogenetic evaluations grouped as ‘non-responders’.

Loss of CCyR

Loss of CCyR is defined as an increase in the Ph+ bone marrow cells to > 0%.

Loss of CCyR must have led to treatment discontinuation because of lack of efficacy (based on the “End of Treatment Phase Disposition” eCRF or “End of Treatment Disposition” eCRF during the Treatment switch phase with Subject status=“lack of efficacy” and Reason of treatment failure = “After start of therapy, loss of CHR, CCyR or PCyR”).

In addition, CML-related death or progression to AP or BC will be considered as loss of CCyR in any case (if they occurred on treatment).

Major cytogenetic response (MCyR)

MCyR is defined as a value of 0% to 35% Ph+ metaphases in bone marrow.

MCyR will be considered as a binary variable with patients achieving MCyR grouped as ‘responders’ and patients not achieving MCyR, patients with missing cytogenetic evaluations grouped as ‘non-responders’.

Loss of MCyR is defined as an increase in the Ph+ bone marrow cells to > 35%. For patients with response = PCyR, this would constitute loss of PCyR.

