5.5 Derivation of response rates and categories

5.5.1 Response rate at a specific time point

The molecular and cytogenetic response evaluations will be summarized by the following mutually exclusive categories which are based on the respective assessment within the time window:

- **Response categories** (sections 5.4.1 and 5.4.2): Patients with an available assessment at that time point (+/- time window) indicating any of the response categories.
- **No response:** Patients with assessment at that time point (+/- time window) indicating 'no response'
- **Missing:** Patients without an evaluable response assessment at that time point (+/- time window). This category is then further split into patients who are ongoing without treatment failure at the beginning of the relevant time window, patients who are ongoing with treatment failure at the beginning of the relevant time window, patients who discontinued due to lack of efficacy, disease progression (PD) or death and patients who discontinued due to other reasons.

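### CCyR is credited from MMR when no marrow was taken, but not when the marrow taken had fewer than 20 metaphases: a small inconsistency in a descriptive endpoint

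*Combined protocol and SAP*

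**What the plan says.** The text is that of the SAP addendum dated 14-Oct-2020. SAP amendment 3.0 (7-Aug-2020) has the same wording on these points.

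- **Marrow schedule (2.7.1.2).** The plan is that "bone marrow aspirate for cytogenetic analyses will be performed as long as subjects have not achieved MMR".
- **Credit rule (2.7.1.2).** From this it follows that "in case no bone marrow aspirate was performed but the subject is in MMR at a specific time-point, the subject is considered to have achieved" the complete response, dated by the MMR.
- **Evaluability (5.4.2).** "Cytogenetic evaluations will be considered for response assessment only if the number of metaphases examined is" at least 20.
- **Binary CCyR (5.4.2).** Alongside those who do not achieve CCyR, the rule has "patients with missing cytogenetic evaluations grouped as" non-responders.
- **Missing (5.5.1).** This category is "Patients without an evaluable response assessment at that time point", allowing for the window.
- **Missing-data handling (2.7.3).** The rule reads "CCyR rates at specific time points: Patients discontinuing the randomized treatment prior to a specific time point due to any reason will be considered as", and the class it assigns is non-response. Nothing is said about a marrow that was taken but could not be evaluated.
- **Baseline stratum (5.1.2.1, also 2.3).** Here a missing sample and one with fewer than 20 metaphases are handled together: an "imputation rule will be applied to derive the missing or non evaluable values", based on BCR-ABL1.

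**The concern.** The credit rests on MMR standing in for CCyR when there is no cytogenetic result. That reasoning does not depend on why the result is absent, but the rule does. Take two patients in MMR at Week 24. One had no marrow and is scored as in CCyR. The other had a marrow with 12 metaphases, all Ph-negative, and is scored as not in CCyR. The second patient supplied more evidence of response and gets the worse score.

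Only patients in MMR can be misclassified in this way. If inadequate samples are equally common in both arms, the loss is larger in the arm with more MMR, and the CCyR difference is pulled towards zero.

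**Working it through.** No figure stated in the plan depends on this rule, so the main check is a trace of the text. The size calculation is illustrative.

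**1. Rule trace for a patient in MMR at a visit**

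| Marrow in the window | Credit in 2.7.1.2 | Cytogenetic result (5.4.2, 5.5.1) | CCyR at the visit |
|---|---|---|---|
| Not performed | Applies | None | Responder, by credit |
| Performed, ≥20 metaphases, 0% Ph+ | Not needed | CCyR | Responder |
| Performed, <20 metaphases, no Ph+ seen | Does not apply | Not evaluable, so missing | Non-responder |

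The third row is an inference from several sections. No single sentence states it. Section 2.7.3 does not change it.

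**2. When the third row can occur**

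- Marrow continues until MMR is achieved, so one may be drawn at the visit where MMR is first shown.
- Table 2-8 lists a marrow aspirate for a biomarker at Week 24 and end of treatment, and Table 2-2 maps end-of-treatment assessments to visits.
- Protocol amendment 2 dropped the 24-weekly marrow for patients in MMR. By 29-Jun-2018, 38 patients had been randomized, and some may have had marrow while already in MMR.
- The Week 24 window is Day 2–253 for cytogenetics and Day 142–211 for PCR. Read literally, an early inadequate marrow could block credit for MMR shown later in the window. Conversely, another evaluable marrow in that window could count, if it is the one selected.

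**3. Illustrative size at Week 24**

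Inputs from SAP section 3.1: 148 asciminib and 74 bosutinib patients, with MMR 35% and 15%. Recalculating the sample size from these rates reproduces the plan's 222 (power 0.903).

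Assumptions not in the documents, and the same in both arms: one third of patients in MMR first reach it at Week 24 and have marrow taken then; 10–20% of those marrows are inadequate.

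Affected share of MMR patients: f = 1/3 × 0.10 to 1/3 × 0.20 = 3.3% to 6.7%.

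Loss in CCyR rate = MMR rate × f:

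- Asciminib: 35% × f = 1.2 to 2.3 points
- Bosutinib: 15% × f = 0.5 to 1.0 points
- Understatement of the difference: (35% − 15%) × f = 0.7 to 1.3 points

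In patients: 148 × 0.35 = 51.8 and 74 × 0.15 = 11.1, total 62.9. A third is 21.0, and 10–20% of that is 2.1 to 4.2 patients over both arms.

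**4. Sensitivity to f**

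Setting f directly at 5%, 10% and 20% gives an understatement of 20 × f = 1.0, 2.0 and 4.0 points. The top value needs one in five of all MMR patients to have an inadequate marrow at that visit, three times the upper f in step 3.

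**5. Denominator**

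These figures use full analysis set planning rates. CCyR rates use the CCyR Analysis Set, which excludes patients in CCyR at baseline (section 2.2). The patient counts in step 3 are therefore upper bounds under the stated assumptions.

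**The case against.** The strongest defence is that the rule was written for marrow skipped by design. The SAP document history describes it as handling marrow assessments missing because MMR had been achieved. On that view a failed marrow is ordinary missing data and non-response is the conservative score, as for a missing PCR. This explains the wording. It does not justify scoring the patient with the inadequate marrow below the one with none, and the SAP itself pools the two situations at baseline.

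The defence is right that the consequence is limited. A reader might infer a material bias against asciminib, for instance because 51.8/62.9 = 82% of affected patients would be on that arm. But 2:1 allocation alone would put 67% there. A reader might also expect the loss to grow at Weeks 48 to 96. The documents do not support that: a patient missed at Week 24 who stays in MMR would normally have no later cytogenetic marrow, and would then be credited. Rates by a visit and time to CCyR are therefore largely delayed rather than lost.

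Two cautions about the remedy also stand. Crediting every inadequate marrow would override one in which Ph-positive cells were seen. And the current text is dated after the primary database lock and review of first results, so a change now is post hoc for Week 24.

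**Conclusion.** The inconsistency is real but minor. As written, the SAP scores a patient in MMR with an inadequate marrow as a CCyR non-responder at that visit, while crediting a patient in MMR with no marrow. It bears mainly on CCyR rates at a visit where MMR is first shown. CCyR is a non-key secondary endpoint with descriptive p-values only (section 2.7.2), and the primary and key secondary MMR tests do not use the credit.

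With equal inadequacy rates in both arms, the difference is slightly understated for the arm with more MMR. The Week 24 figure of 0.7–1.3 points rests on the two assumed fractions and on planning rates for a somewhat different population. It indicates scale and is not an estimate. The rule cannot create a false claim of benefit for the arm with more MMR.

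One limit on the source: the file ends with the opening of a further SAP document history, so the wording of any later version could not be checked.

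**What to change.** In section 2.7.1.2, change the condition from no aspirate having been performed to no evaluable aspirate being available. Define that as either not performed, or fewer than 20 metaphases examined with no Ph-positive metaphase seen. Leave the rest of the sentence as it is. This brings the rule into line with section 5.1.2.1 without overriding a marrow that showed Ph-positive cells.

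Set the change in writing before the 96-week analysis. The primary database is already locked, so keep the reported Week 24 rule and show any re-run under the new one as a labelled post-hoc sensitivity analysis.

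The cost is a few words of text, minor reprogramming and one extra sensitivity table. No new data collection is needed, provided the Ph-positive count was recorded for samples below 20 metaphases, which should be confirmed.
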